## INVESTIGATOR STUDY PLAN - REQUIRED

*administer a client satisfaction measure that will unblind the Co-I to which subjects are in the waitlist control group.)*

**Intervention:** Participants randomized to receive the intervention will be provided weekly individual treatment with one of four ASL-fluent study clinicians, based on preferred location and transportation needs. Each participant in this condition will receive 12 one-hour sessions of treatment. The maximum length of treatment will be capped at six months and the total number of completed sessions will be tracked as a measure of participant adherence. Therapists will treat an approximately equal percentage of participants, in order to minimize confounding of therapist effect and study site on treatment outcome.

Treatment sessions will be provided in each study clinician's private practice office, in direct response to findings from the PI's NIDCD R21, which revealed Deaf people's communal fear of academic research settings due to a long history of mistreatment by doctors and biomedical researchers (e.g., eugenics) (Anderson, Wolf Craig, & Ziedonis, 2016; Anderson et al., 2018; Anderson, Wolf Craig, & Ziedonis, 2017; McKee, Schlehofer, & Thew, 2013; Lane, 2005). As such, study therapists must be independently licensed in MA and will take on professional liability for the cases that they see. Study therapists will be compensated \$80 a session – a rate that is comparable to the average insurance reimbursement for individual therapy sessions with Deaf clients. Proof of sufficient liability insurance will be obtained from each study therapist prior to beginning the RCT.

**Waitlist Control:** Following the final assessment at 16 weeks, waitlist control participants will be offered the opportunity to receive the 12-session *Seeking Safety + Signs of Safety* protocol. This 16 week waiting period is equivalent to the current waitlist to receive psychotherapy services through the PI's outpatient clinic. Participants who are randomized to the waitlist, but express immediate need for services during the waitlist period will be provided referral to non-study treatment options (i.e., supportive psychotherapy provided either directly in ASL or with an ASL interpreter) and subsequently coded as a non-retained waitlist participant.

**Assessments.** Using measures validated in the general population, we will assess clinical outcomes and mechanisms of change at baseline, two within-treatment time points (after session 4 and 8), immediate post-treatment (within one week after session 12), and one-month follow-up. The Study Assessor, blind to study condition, will administer assessments as structured ASL interviews via videophone. (*Note: the Study Assessor will remain blind to study condition until the end of the post-treatment assessment, at which point she will administer a client satisfaction measure that will unblind the Co-I to which subjects are in the waitlist control group.*) Any Likert-scale-type questionnaires that are administered during the study interview will be presented directly in American Sign Language; the interviewer will also display a visual aid of the response options to assist participants in keeping track of changing Likert scales between various measures.

Compared to in-person assessments, our proposed method of remote videophone assessment is more responsive to Deaf people's transportation barriers, financial barriers, and technology preferences. This videophone method was used successfully in the *Signs of Safety* one-arm pilot study, as well as other previous studies with Deaf individuals. Participants will be compensated

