### 6. INCLUSION AND EXCLUSION CRITERIA\*

We aim to enroll 60 Deaf adults from New England using rolling recruitment across two years. Based on the KL2 pilot results, we predict that 45 of 60 participants (conservative retention rate of 75%) will complete end-of-treatment assessment.

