## INVESTIGATOR STUDY PLAN - REQUIRED

\$25 at each assessment time point (1 hour for baseline, 30 minutes for follow-up) via a Visa gift card sent to the mailing address of their choice. Participants not retained in treatment will be contacted for follow-up assessments at each scheduled time point for intent-to-treat analyses and examination of potential biases due to non-adherence.

In the control condition, assessment will occur at baseline, week 4, week 8, week 12 (to approximate immediate post-treatment), and week 16 (to approximate one-month follow-up). Such repeated assessment in the control arm will allow us to quantify and control for participants' natural change over time and assessment reactivity.

**Feasibility measures:** We will collect data on recruitment, retention, and other key aspects of feasibility (Table 3). We will augment client satisfaction measures with questions specific to *Signs of Safety*. All intervention sessions will be videotaped, with 25% (3 sessions per participant) rated for fidelity on an ongoing basis by the Fidelity Consultant To quickly correct fidelity concerns, capture fidelity throughout the treatment process, and evaluate impact of site differences on study findings, one tape will be randomly selected from sessions 1 - 4; one from 5 - 8; and one from 9 - 12. Sessions will be rated with the *Seeking Safety Adherence Scale* plus the *Signs of Safety Fidelity Scale*.

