## INVESTIGATOR STUDY PLAN - REQUIRED

available outcome data, we will examine their sociodemographic characteristics to compare with those participants who do have available outcome data.

**Analytic plan for feasibility.** For quantitative feasibility outcomes, we will calculate descriptive statistics for the overall sample and separated by treatment arm: mean number of participants screened and enrolled per week; rate of retention; clinician treatment fidelity (rates of integrity, rates of differentiation); participant adherence (number of sessions completed, rates of between-session homework completion); and assessment process (proportion of assessments completed, mean duration of assessment calls). We will compare retention, fidelity, and adherence between the two treatment conditions using chi-square and t-tests.

**Precision of rate estimation:** Based on pilot results, we anticipate at least 45 of the 60 enrolled participants will be retained through immediate post-treatment. See *Section 25. Local Number of Subjects* for more information on the estimated post-attrition sample size and retention rate.

For qualitative feasibility outcomes, open-ended responses to the *End of Session* and *End of Treatment Questionnaires* will be analyzed in *ATLAS.ti* for themes regarding satisfaction with each study arm (e.g., *What comments or suggestions do you have about today's session?*, *How could this treatment be more helpful to you?*). We will use an iterative, grounded theory approach employing two major techniques: (1) content analysis, where the number of similar responses will be tallied and described; and, (2) a summary of the answers to questions outlined by Casey (e.g., *What ideas will be especially useful for the intervention?*).

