### 25. LOCAL NUMBER OF SUBJECTS

We will enroll 60 Deaf adults from Massachusetts. Based on pilot results, we anticipate at least 45 participants will be retained through immediate post-treatment (60 enrolled participants x a conservative 0.75 retention rate), or 22 participants per treatment arm. This post-attrition sample size falls within the guidelines for a pilot RCT behavioral therapy study - “15 to 30 participants per cell” - and is “based on the pragmatics of recruitment and the necessities for examining feasibility.”

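### Retention is coded on different grounds in the two arms, so the planned between-arm retention test cannot be read as a comparison of loss to follow-up

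*Combined protocol and SAP*

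**What the plan says.** Four places bear on retention.

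- **Section 11, Waitlist Control.** Waitlist participants who "express immediate need for services during the waitlist period will be provided referral to non-study treatment options" and are then "subsequently coded as a non-retained waitlist participant". The trigger is an expressed need followed by referral. Neither uptake of outside care nor a missed assessment is required.
- **Sections 6 and 25.** Section 6 ties retention to an assessment: "we predict that 45 of 60 participants (conservative retention rate of 75%) will complete end-of-treatment assessment". Section 25 uses the same rate ("60 enrolled participants x a conservative 0.75 retention rate") for participants retained through immediate post-treatment, "or 22 participants per treatment arm".
- **Section 11, Assessments.** "Participants not retained in treatment will be contacted for follow-up assessments at each scheduled time point for intent-to-treat analyses". Here a person can be non-retained and still be assessed.
- **Section 13, Analytic plan for feasibility.** "We will compare retention, fidelity, and adherence between the two treatment conditions using chi-square and t-tests". No definition of retention is given for this comparison.

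Section 6 asks participants in both arms to refrain from concurrent formal psychotherapy. No section gives a retention code for a treatment-arm participant who uses it. The deterioration provisions in Sections 10 and 14 allow withdrawal and outside referral, with an option to return. They are not specific to an arm and state no retention code.

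**The concern.** A waitlist participant who is referred out and then completes the week-12 assessment counts as retained under Section 6 and as non-retained under the Waitlist Control rule. The need-triggered code is written for the waitlist arm only, and that arm waits 16 weeks without study treatment. A difference in coded retention could therefore reflect referrals, missing data, or both, and the test cannot tell them apart.

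Section 4 names retention in both arms as a key aspect of feasibility and says that the results will support a full-scale trial. A control-arm rate that mixes referral with lost data is a poor guide to attrition in that trial. There is also a practical ambiguity: the plan does not say outright that referred waitlist participants keep being assessed, and the promise of continued contact is worded for people who leave treatment.

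**Working it through.** **Inputs from the documents.** 60 enrolled and 75% retention (Sections 6 and 25). No allocation ratio is written; 22 retained per arm implies 1:1, so 30 per arm.

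**Assumptions.** Two-sided alpha of 0.05 (none is stated for this test). True week-12 completion is the same in both arms. A share *f* of waitlist completers is referred and recoded. Nobody in the treatment arm is recoded, except where stated below. The documents give no value for *f*.

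**The plan's own figure.** 60 × 0.75 = 45, or 22.5 per arm, reported as 22. It reproduces.

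**Effect of the code.** Coded waitlist retention is 0.75 × (1 − *f*), so the artificial difference is 0.75 × *f*. The rejection rate comes from exact enumeration of two independent binomials with n = 30 each, using the Pearson chi-square test.

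| *f* (assumed) | Coded waitlist retention | Artificial difference (points) | Rejection rate |
|---|---|---|---|
| 0 (one definition) | 75% | 0 | 4.9% |
| 5% | 71.3% | 3.8 | 6.1% |
| 10% | 67.5% | 7.5 | 9.6% |
| 20% | 60.0% | 15.0 | 23.0% |
| 30% | 52.5% | 22.5 | 43.8% |

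From *f* = 10% upward, nearly all rejections show higher retention in the treatment arm. With the Yates correction the rates are lower: 2.5% at *f* = 0, 5.8% at 10%, about 16% at 20% and about 34% at 30%. If true completion is 70% to 90% rather than 75%, *f* = 20% gives uncorrected rejection rates of 20% to 43%.

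**A fixed example.** Let 22 of 30 complete week 12 in each arm, and recode 8 waitlist completers, giving 22/30 against 14/30. The pooled proportion is 36/60 = 0.60. Chi-square = (8/30)² / (0.60 × 0.40 × 2/30) = 0.0711/0.0160 = 4.44, p = 0.035 (Yates 0.065). Recoding 7 gives p = 0.063.

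**Direction.** Suppose a share *g* of treatment-arm completers, having stopped sessions, is also coded non-retained. The coded difference, treatment minus waitlist, becomes 0.75 × (*f* − *g*). It vanishes when *g* = *f* and reverses when *g* > *f*: with *f* = 10% and *g* = 20% it is −7.5 points. The documents fix neither share, nor whether *g* is counted at all.

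**The case against.** The strongest reply is that retention may mean remaining in the assigned condition. Section 5.d describes pilot participants retained in treatment as having completed both the sessions and the end-of-treatment assessment, and Section 11 speaks of people not retained in treatment. On that reading, a waitlist participant referred to psychotherapy has left the assigned condition much as a treatment-arm participant who stops sessions has. The reading is reasonable, but the plan does not adopt it. Sections 6 and 25 fit an assessment-based meaning better, and Section 13 does not choose.

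Other safeguards limit the harm. Section 13 already reports the proportion of assessments completed, by arm and separately from retention, so loss of data can be seen whatever the code. It also keeps all randomized participants in the analysis. Section 11 schedules control assessments through week 16 with no exception for referred participants. These points stand. They reduce the consequence but do not make the retention test interpretable.

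A reader might infer more than the documents support:

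- **That the test is biased against the waitlist by definition.** The rule has no effect if nobody is referred, or if those referred would have missed week 12 anyway. The net direction is open, as shown above.
- **That treatment-arm participants who stop sessions are never counted as non-retained.** No section says so, and the wording of Section 11 suggests that such a status exists.
- **That the highest-need controls leave the outcome data and the treatment effect shrinks.** Nothing says that the code ends assessment. If they stay in assessment while receiving outside care, control outcomes could also improve.

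**Conclusion.** The concern holds in a limited form. Retention is not defined for the Section 13 comparison. The waitlist arm has a referral-based code that does not depend on assessment, while the planning rate is assessment-based. The between-arm chi-square result therefore cannot be read as a comparison of loss to follow-up.

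The size depends on an unknown referral share. At 5% the rejection rate barely moves from nominal (6.1% against 4.9%); at 20% to 30% it reaches 23.0% to 43.8%. These figures assume equal true completion of 75%, 30 per arm, two-sided 0.05, no recoding in the treatment arm, and that everyone recoded actually completes week 12. They show what the rule could do, not what is likely.

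The issue affects a feasibility outcome. The clinical comparisons would be affected only if staff took the non-retained code to mean that assessment stops. The plan should be clarified before the retention comparison is run.

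**What to change.** In Section 13, define retention for the between-arm comparison identically in both arms: completion of the week-12 assessment, with week-16 completion reported separately.

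In Sections 11 and 13, record treatment discontinuation, and referral to or use of outside services, as separate variables in both arms, and report them beside retention. Replace the waitlist non-retained code with the referral variable.

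State in Section 11 that referred waitlist participants keep their scheduled assessments and stay in the intent-to-treat analysis. This agrees with the control-arm assessment schedule in Section 11 and the analysis set in Section 13.

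The referral procedure itself is unchanged. The cost is wording and a few database fields; the control-arm assessments are already scheduled and compensated.

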## INVESTIGATOR STUDY PLAN - REQUIRED

revising the therapist companion guide. We will then develop a training program for *Signs of Safety* and certify four study clinicians.

We propose to conduct a **two-arm pilot RCT of *Signs of Safety***. We aim to enroll 60 Deaf adults with past-month PTSD and past-month alcohol consumption to participate in 12 weekly individual treatment sessions. The pilot RCT will compare the 12-session protocol of *Seeking Safety + Signs of Safety* toolkit with an assessment-only waitlist control. Across conditions, assessment will occur at baseline, week 4, week 8, immediate post-treatment/week 12, and one-month follow-up/week 16. We will analyze key aspects of feasibility for both study arms (e.g., recruitment, retention, assessment process). Primary clinical outcomes at immediate post-treatment and one-month follow-up are past 30-day alcohol use frequency/quantity and past 30-day PTSD severity. Exploratory analyses will be conducted to examine potential moderators and mediators of change (e.g., motivation for treatment, provider cultural competency, coping skills, self-compassion, understanding of health information) leading to positive outcome. Results from this study will produce feasibility and preliminary efficacy data to support for a full-scale RCT to evaluate *Signs of Safety*, and a community-engaged model for conducting RCTs with Deaf participants.

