**9. STUDY TIMELINES\***

The total duration of the study will be 3 years (Table 1). Primary analyses will be completed by end of year 3. We anticipate that it will take 2 years of rolling recruitment to enroll all study participants (Table 2). Participation in the study will last at most 6 months.

Table 1: Study Timeline	YEAR: QUARTER:	1				2				3			
		1	2	3	4	1	2	3	4	1	2	3	4
Create final, professional iteration of Signs of Safety toolkit													
Develop clinician training and supervision program													
Train and certify study clinicians (+back-up clinician)													
Pilot RCT preparation, IRB approval, registration on ClinicalTrials.gov													
Pilot RCT: Rolling recruitment, enrollment, and randomization (n=60)													
Ongoing fidelity rating, data entry, and analyses for safety monitoring													
Final data analyses, report/paper writing, and R01 preparation													

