## INVESTIGATOR STUDY PLAN - REQUIRED

YEAR 2											
1	2	3	4	5	6	7	8	9	10	11	12
Rolling recruitment and study period (recruitment rate ≈ 3 per month; length of study period ≈ maximum 6 months per participant)											
E = 18 ✓ = 0	E = 18 ✓ = 3	E = 18 ✓ = 6	E = 18 ✓ = 9	E = 18 ✓ = 12	E = 18 ✓ = 15	E = 18 ✓ = 18	E = 18 ✓ = 21	E = 18 ✓ = 24	E = 18 ✓ = 27	E = 18 ✓ = 30	E = 18 ✓ = 33
YEAR 3											
1	2	3	4	5	6	7	8	9	10	11	12
No recruitment; study period only (length of study period ≈ maximum 6 mo./participant)											
E = 18 ✓ = 36	E = 18 ✓ = 39	E = 18 ✓ = 42	E = 15 ✓ = 45	E = 12 ✓ = 48	E = 9 ✓ = 51	E = 6 ✓ = 54	E = 3 ✓ = 57	E = 0 ✓ = 60	Study wrap-up		

 
• Final follow-up
 
• Data analyses
 
• Optional exit interview
 
											

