**Table 3: Clinical Outcome Measures**

Variable	Measure (primary outcome measures noted in bold font)	Time Point					
		Screen	Baseline/ Pre-TX	Week 4	Week 8	Week 12/ Post-TX	1-month Follow-up
Alcohol Use and Craving	AUD Identification Test (AUDIT)	X					
	Alcohol Timeline Followback		X	X	X	X	X
	Comprehensive Effects of Alcohol Scale - Brief		X	X	X	X	X
	Penn Alcohol Craving Scale (PACS)		X	X	X	X	X
PTSD	PTSD Checklist for DSM-5 (PCL-5)	X	X	X	X	X	X
	Trauma Symptom Checklist – 40 (TSC-40)		X			X	X
Behavioral Health	Behavior and Symptom Identification Scale (BASIS-24)		X			X	X
Mediators and Moderators of Change	Coping Self-Efficacy Scale		X	X	X	X	X
	Self-Compassion Scale – Short Form		X	X	X	X	X
	Ask, Understand, Remember Assessment (AURA)		X	X	X	X	X
	Stages of Change Readiness and Treatment Eagerness Scale (SOCRATES 8A)		X			X	X
	Healthcare Provider Cultural Competency		X			X	X

**Identification of serious psychiatric problem.** If at any time a participant is identified as having a serious psychiatric problem that requires a higher level of care than our study can provide, this concern will be immediately reported to the PI, who will provide referral and bridging to appropriate treatment options for stabilization. Once stabilized, the participant will have the option to return to our study.

**Clinical emergencies.** Study clinicians and Study Assessor will contact 911 in the event of a dangerous situation (or the PI for less urgent clinical crises), and will complete adverse events

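### Outcome visits are timed by week in some sections and by session in others, and no section says which clock governs treated participants whose 12 sessions run late or are never completed

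*Combined protocol and SAP*

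**What the plan says.** **By week.** Section 4 states: "Across conditions, assessment will occur at baseline, week 4, week 8, immediate post-treatment/week 12, and one-month follow-up/week 16". Section 10, Table 3 (Clinical Outcome Measures) uses weeks 4 and 8 and one column headed "Week 12/ Post-TX". Section 13 compares the arms at post-treatment, equated with week 12, and at the end of follow-up, equated with week 16.

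**By session.** Section 11 (Assessments) gives "two within-treatment time points (after session 4 and 8), immediate post-treatment (within one week after session 12), and one-month follow-up". Section 14 also places the PTSD collections after sessions 4 and 8.

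**Mixed.** Section 11 (Measures of clinical outcome) repeats the Assessments sentence with weeks 4 and 8 in place of sessions 4 and 8, but keeps session 12 for post-treatment.

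**Controls.** Section 11 (Assessments) fixes them at weeks 4, 8, 12 and 16, and calls the last two approximations to post-treatment and one-month follow-up. They are then offered treatment: "Following the final assessment at 16 weeks, waitlist control participants will be offered the opportunity to receive the 12-session" protocol.

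**Late or incomplete treatment.** Section 11 (Intervention) says: "The maximum length of treatment will be capped at six months". Participants not retained in treatment are to be contacted at every point on the schedule, without saying whether the schedule is in weeks or sessions. No section gives a precedence rule or a visit window, apart from the week allowed after session 12.

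**The concern.** With weekly sessions and none missed, the two clocks agree to within about a week. They separate once sessions are missed, which the plan allows for.

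If the session wording is followed, late treated participants are assessed longer after randomisation than controls at both primary time points. Section 11 relies on the control assessments to account for natural change over time, and that needs a shared clock. The bias could go either way: natural improvement would favour treatment, and natural worsening would count against it.

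If the week wording is followed, the comparison is concurrent, but the post-treatment visit falls in mid-treatment for anyone delayed. These are two different estimands under one label. Section 13 intends the effect sizes for planning the larger trial, so its planners need to know which one was estimated.

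**Working it through.** The plan states no figure for visit timing, so there is none to reproduce. The check is calendar arithmetic, followed by an illustration on assumed inputs.

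**1. Gap between arms at post-treatment on the session clock.** Gap = (week of session 12, plus 0 to 1 week) minus 12.

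- Session 12 at week 12: 12 to 13, minus 12 = 0 to 1 week.
- Session 12 at week 16: 16 to 17, minus 12 = 4 to 5 weeks.
- Six-month treatment cap (about week 26): 26 to 27, minus 12 = 14 to 15 weeks.
- If Section 9's six-month limit on participation governs, treatment ends by about 26 − 4 = week 22, and the gap is about 22 − 12 = 10 weeks.

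The one-month follow-up shifts by about the same amount against week 16. On the week clock, a participant at the cap pace would have had 12 × 12/26 ≈ 5.5 sessions at the week-12 visit.

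**2. Whether the models correct for it (Section 13).** Model 1 uses period indicators and Model 3 (PCL-5) uses visit indicators, so neither sees elapsed time. Model 2 has a week term, but for alcohol only, and controls have no data after week 16.

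**3. Drinking series on the session clock.** Section 13 wants daily data throughout the treatment or waitlist period. Section 11 sets each Timeline Followback recall at 30 days. With sessions evenly spread and three calls during or at the end of treatment, uncovered days = 7 × weeks − 3 × 30:

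| Weeks to session 12 | Treatment days | Uncovered |
|---|---|---|
| 13 | 91 | 1 |
| 16 | 112 | 22 |
| 20 | 140 | 50 |
| 26 | 182 | 92 |

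The past-30-day endpoint at each visit is fully covered. The gaps affect only the weekly series for Models 1 and 2. The drinking reports at session check-in (Section 14) do not exist for controls.

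**4. Possible size of the PCL-5 bias (assumed inputs).** The documents give no missed-session rate and no natural drift. Assume that retained participants miss each weekly session independently with probability p, and that PCL-5 drifts between 1 point per month worse and 2 points per month better.

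- Mean delay = 12/(1 − p) − 12, capped at week 26.
- Proportion reaching session 12 after week 16 = P(Bin(16, 1 − p) < 12).
- Bias = delay/4.348 × drift, with plus favouring treatment.
- Dilution on the week clock at week 12 = 10 × p, if a 10-point effect builds up evenly over sessions (also assumed).

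| p | Mean delay, weeks | After week 16 | Drift bias, points | Week-12 dilution, points |
|---|---|---|---|---|
| 0.10 | 1.3 | 1.7% | −0.3 to +0.6 | 1.0 |
| 0.20 | 3.0 | 20.2% | −0.7 to +1.4 | 2.0 |
| 1/3 | 6.0 | 66.1% | −1.4 to +2.8 | 3.3 |

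From Section 13's standard deviation of 21.2 and 22 completers per arm, SE = 21.2 × √(2/22) = 6.39. The largest bias is 2.75/6.39 = 0.43 SE. If the 25% not retained are called by week, the arm-average delay is 0.75 of that shown.

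**The case against.** The strongest reply is that the plan already has a workable scheme. Both passages in Section 11 that give an operational rule for post-treatment in treated participants use session 12. Section 14 ties follow-up to the end of treatment. The control weeks are expressly approximations, so the week labels in Sections 4, 10 and 13 could be nominal. This reading is coherent, and the plainest contradiction is then at weeks 4 and 8, which are not the primary comparison times. But it does not settle the matter. Section 4 applies weeks to both arms, and the reading gives no visit time for someone who stops treatment before session 12, in a trial that plans for 25% attrition.

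A reader might infer that the week clock is correct and the session wording a mistake. The documents do not support that. In every scenario above, the week-12 dilution from using weeks exceeds the largest drift bias it would remove (1.0, 2.0 and 3.3 points against 0.6, 1.4 and 2.8). Week 16 is kinder to the week clock: by the same assumptions, dilution there is about 0.0, 0.3 and 1.3 points. The choice is between estimands.

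A reader might also infer that the primary comparison is seriously biased. The 14 to 15 week gap is an extreme; under the assumed model, fewer than 1% would fail to reach session 12 by week 26 even with one third of sessions missed. Section 5 reports that retained pilot participants completed all 25 sessions, although it does not give their pace.

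**Conclusion.** The week and session timings conflict in the text, and no rule covers late or incomplete treatment. That much rests on the documents alone. So do the possible gap of 4 to 5 weeks when session 12 falls at week 16 and Model 3's inability to account for it. The 22 to 92 uncovered drinking days for 16 to 26 weeks of treatment need only the assumption of evenly spread sessions.

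The number of participants affected is unknown. The average PCL-5 bias is modest, at most about 0.43 of a standard error, and that figure rests wholly on assumed missed-session rates, independent misses and assumed drift. The point is mainly one of interpretability: the plan should say what its week-12 and week-16 effect sizes estimate. It is worth settling beforehand, because visits held at inconsistent times cannot be re-timed afterwards.

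Two neighbouring matters are separate. The satisfaction measure unblinds the assessor after the post-treatment assessment whichever clock is used ("the Study Assessor will remain blind to study condition until the end of the post-treatment assessment"). The six-month limit on treatment also sits awkwardly with Section 9 ("Participation in the study will last at most 6 months"; Table 2: "length of study period ≈ maximum 6 months per participant"), since six months of treatment plus one month of follow-up is about seven. The sponsor must reconcile those passages.

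**What to change.** 1. **Name one clock.** Reconcile Sections 4, 10, 11, 13 and 14 to one governing clock for the primary between-arm comparison, with a stated window that also applies to participants not retained in treatment. Counting weeks from randomisation in both arms gives concurrent controls, but at week 12 it measures treatment received to date, and week 16 is not one month after treatment for those delayed. The sponsor should choose and name the estimand. The cost is protocol wording. If outcome calls go by week while Section 14 stays by session, there could be up to four extra PTSD collections per delayed participant, in the treated arm only. That would weaken the matched repeated assessment on which Section 11 relies. Section 14 should therefore be reconciled with whichever clock is chosen; no monitoring rule is proposed here.

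2. **Extend the drinking recall.** In Section 11, run each Timeline Followback back to the previous assessment date. This stays within the 30 to 360 day range the plan gives for the instrument. The cost is longer recall for some: up to 28 + 14 = 42 days on a week clock with a window of plus or minus one week, and more for delayed participants on a session clock.

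3. **Record dates and add a sensitivity analysis.** Record actual assessment dates and sessions completed by week 12, and add a PCL-5 analysis using elapsed time since randomisation. State its limit: controls have no data after week 16, so later treated visits have no concurrent comparison. The cost is small.
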